# **Eligibility**

Ages Eligible for Study: 18-65

Genders Eligible for Study: Female

### **Inclusion Criteria**:

- 1. A diagnosis of IC/BPS defined based on AUA guidelines as the following: an unpleasant sensation (pain, pressure, discomfort) perceived to be related to the urinary bladder, associated with lower urinary tract symptoms of more than 6 months duration, in the absence of infection or identifiable causes, documented history or patient reported.
- 2. Only those patients with moderate to severe IC/BPS will be included in the study.
- 3. Able to provide informed consent to participate in the study and comply with study requirements
- 4. Able to provide written authorization for use and release of health and research study information
- 5. Written documentation of being provided California's Experimental Subject's Bill of Rights
- 6. Females ≥18 and ≤ 65 years of age previously diagnosed with interstitial cystitis/ bladder pain syndrome (IC/BPS) for a duration of greater than 6 months
- 7. Female patients of child-bearing potential must have a negative serum pregnancy test at Screening and use birth control while in the study.
- 8. O'Leary-Sant Interstitial Cystitis Symptom and Problem Indexes (OSPI) score ≥ 18
- 9. No history of any cancer.
- 10. No bacterial cystitis in previous 1 month
- 11. No active herpes in previous 3 months
- 12. Never treated with cyclophosphamide
- 13. No neurogenic bladder dysfunction (due to a spinal cord injury, stroke, Parkinson's disease, multiple sclerosis, spina bifida or diabetic cystopathy)
- 14. Absence of bladder, ureteral or urethral calculi for previous 3 months

#### **Exclusion criteria:**

- 1. Symptoms are relieved at one month reevaluation visit after receiving IC/BPS behavior modification advice at screening visit.
- 2. Symptoms are relieved by antimicrobials, antibiotics, or other medications for IC/BPS
- 3. Pregnant women, lactating mothers, nursing mothers, women suspected of being pregnant and woman who plan to be pregnant during the course of the clinical trial
- 4. Males
- 5. Patients with inadequate renal, hepatic, or cardiac function
- 6. Patients with history of gross hematuria within 2 years.
- 7. Patients with the following medical history: Lower urinary tract anatomical anomaly, pelvic radiotherapy, or active genital herpes
- 8. Patients with a history of tuberculosis (TB), recent exposure to TB, or recent travel to TB endemic regions. Patients should have a recent negative PPD (or negative CXR) prior to receiving treatment.
- 9. Patients who have undergone cystoscopy under anesthesia with bladder biopsy, hydrodistension, or fulguration of Hunner's ulcer within 3 months
- 10. Patients taking the following treatments for interstitial cystitis at Screening: Intravesical BCG, corticosteroid therapy, cyclosporine, or TNF-alpha inhibitors.
- 11. Patients with a history of receiving live vaccine including Flumist® influenza vaccine in the past 3 months.
- 12. Patients with a history of allergic or anaphylactic reaction to a therapeutic or diagnostic monoclonal antibody or IgG-fusion protein.

[figure not shown]
- 13. Patients with a history of alcohol, analgesic or drug abuse within 2 years of Screening.
- 14. Patients with a history of any cancer.
- 15. Patients with a history of active Hepatitis B, Hepatitis C, or Human Immunodeficiency Virus (HIV) infection, or who are known carriers (Hepatitis B).
- 16. Patients with a history of invasive fungal infections, recent travel to regions endemic for the following invasive fungal infections: San Joaquin Fever, aspergillosis, histoplasmosis, candidiasis, coccidiodomycosis, blastomycosis, and pneumocystosis.
- 17. Patients with a history of diabetes mellitus.
- 18. Patients with a history of a neurologic disease included but not limited to central demyelinating diseases, including multiple sclerosis; and a history of peripheral demyelinating disease, including Guillain-Barre syndrome.
- 19. Other severe acute or chronic medical or psychiatric condition or laboratory abnormality that may increase the risk associated with study participation or investigational product administration or may interfere with the interpretation of study results and, in the judgment of the Investigator, would make the patient inappropriate for entry into this study.

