### **Study Design**

Patients enter a one month Screening period to assess inclusion/exclusion criteria, sign informed consent, and determine study eligibility. At the initial screening visit, patients will be instructed in behavior modification techniques to improve IC/BPS symptoms.  Patients are reassessed at least one month later for inclusion/exclusion criteria and determine study eligibility. Patients who do not improve with standard IC/BPS advice and pass clinical and laboratory screening can be participants in the study. Baseline evaluation of the included patients will be done with the O'Leary-Sant Interstitial Cystitis Symptom Index and Problem Index (OSPI). At the baseline visit (week 0), all eligible IC/BPS patients will be randomized in a blinded fashion to receive in a 2:1 ratio either SQ certolizumab pegol 400mg or SQ placebo at weeks 0, 2, 4 followed by a maintenance dose at 8 weeks. The length of the study will be 18 weeks. The effectiveness of certolizumab pegol will be assessed at week 2, 4, 10, and 18 using GRA, ICSI, ICPI, and the numeric pain and urgency scale. After subjective evaluation of efficacy and safety in the initial 30 patients, the total study sample size will be 42 study patients.

A midstream urine will be collected at baseline and weeks 2, 4, 10, and 18 from all participants. Quest Diagnostics Nichols Institute, San Juan Capistrano, CA or similar lab will perform an ELISA TNFα and creatinine levels on these samples.

Pilot Study Evaluating the Efficacy of CZP for Interstitial Cystitis Study Flow Chart

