# **Trial Schedule**

	Screen	>One Month Reevaluation	Baseline	Visit 1	Visits 2, 3	Visit 4	Phone Follow- up 	Phone Follow- up 
Study Day	-37	-7	0	14	28,56	70	98	126
Study Week	-5	-1	0	2	4,8	10	14	18
Study								
procedures:								
Obtain Informed Consent	X							
Medical History	X							
Medication Review	X	X	X	X	X	X		
Vitals 	X	X	X	X	X	X		
Physical Exam	X							
OSPI 	X	X						
anti-HCV, HBsAG		X						
PPD		X						X
CBC						X		X
Urinalysis	X	X	X	X	X	X		
Urine Culture		X	X	X	X	X		
Urine Pregnancy Test		X						
Eligibility Assessment	X	X						
Dispense Study Drug			X	X	X			
Injection Site Evaluation 			X	X	X			
Adverse Events			X	X	X	X	X	X
GRA 				X	X	X		X
ICSI, ICPI 				X	X	X		X
Numeric scale of pain and urgency	X	X	X	X	X	X		X

- 1. Height, weight, blood pressure, pulse, temperature
- 2. O'Leary-Sant Interstitial Cystitis Symptom Index and Problem Index
- 3. Monitor subjects for systemic and local hypersensitivity reactions for one hour after injection

- 4. Global response assessment
- 5. Interstitial Cystitis Symptom Index, Interstitial Cystitis Problem Index
- 6. In-office visit if determined to be clinically necessary

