### **Safety Evaluation**

Patients will be assessed at office visits and by continuous availability by phone for adverse events. Adverse effects may include rhinitis, headache, rash, pruritus, injection site reaction, infections, tuberculosis, cancer, and demyelinating diseases.

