#### **Stopping Criteria for Adverse Events**

#### **Serious infections:**

These include TB and infections caused by viruses, fungi, or bacteria. Symptoms related to TB include cough, low-grade fever, weight loss, or loss of body fat and muscle.

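### Exclusion 8 accepts a clear chest X-ray in place of a negative PPD without saying when, so as worded a PPD-positive woman can meet the TB rule and be randomised

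*Protocol*

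**What the plan says.** Exclusion 8 in the protocol has two parts. The first excludes on history: "Patients with a history of tuberculosis (TB), recent exposure to TB, or recent travel to TB endemic regions". The second is the test requirement: "Patients should have a recent negative PPD (or negative CXR) prior to receiving treatment". The PPD and the film are joined by a plain *or*, and the verb is *should*.

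The Trial Schedule marks a PPD twice, at re-evaluation (day -7) and at the last follow-up (day 126). It has no chest X-ray row.

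Two other provisions could keep a woman out:

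- Exclusion 19 covers other severe conditions or laboratory abnormalities that may raise risk and which, "in the judgment of the Investigator, would make the patient inappropriate for entry into this study".
- Study Design states: "Patients who do not improve with standard IC/BPS advice and pass clinical and laboratory screening can be participants in the study". It gives no TB pass standard of its own.

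The protocol treats TB as a hazard of treatment. Safety Evaluation says: "Adverse effects may include rhinitis, headache, rash, pruritus, injection site reaction, infections, tuberculosis, cancer, and demyelinating diseases". TB also appears under the stopping criteria, with its signs: "Symptoms related to TB include cough, low-grade fever, weight loss, or loss of body fat and muscle". The SAP does not deal with TB screening.

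**The concern.** The skin test is the only TB test scheduled before the first dose, and every candidate has one. A reader would expect a positive result to have a stated consequence. In the visible text it has none: no passage makes a positive PPD exclusionary or says what to do after one. The *or* in exclusion 8 lets a clear film satisfy the requirement whatever the PPD showed.

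At stake is whether a woman with a positive TB test can receive a drug for which the protocol itself lists TB as an adverse effect, with the outcome depending on one investigator's judgement and not on a written rule. The question is one of patient safety and of applying eligibility consistently. It does not affect the primary analysis.

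**Working it through.** No formula applies to the rule itself, so the check is to apply the text to each combination of results. Take a woman with no past TB, no recent contact and no recent endemic travel, so that the history part of exclusion 8 does not remove her.

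| Day -7 PPD | Film | Test rule as worded | If the film is only a fallback | After the amendment below |
|---|---|---|---|---|
| Negative | any or none | met | met | met |
| Positive | clear | **met** | not met | not met |
| Positive | not clear, or none | not met | not met | not met |
| Not done or not readable | clear | met | met | met |
| Not done or not readable | not clear, or none | not met | not met | not met |

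Only the second row depends on the reading. There the literal *or* is satisfied by the film alone.

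Next, what else could stop the woman in that row:

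- Exclusion 19 can, if the investigator judges that her result makes her unsuitable. It does not oblige the investigator to do so.
- The Study Design requirement to pass screening can, if the investigator counts a positive PPD as a failure. The only written TB standard to apply is exclusion 8, which she meets.
- The history part of exclusion 8 could be stretched to treat a positive PPD as a history of TB, but the text does not say that.

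If none of these is used, she is randomised 2:1, a 2/3 chance of certolizumab pegol. In a trial of 42 that ratio gives 42 × 2/3 = 28 active and 42 × 1/3 = 14 placebo.

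Last, what the schedule provides after entry:

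- Doses are at weeks 0, 2, 4 and 8, which are days 0, 14, 28 and 56: 4 doses.
- The two PPDs are 126 − (−7) = 133 days apart. All 4 doses fall between them, with no TB test scheduled in the interval.
- The second PPD comes 126 − 56 = 70 days after the last dose.
- Vitals ("Height, weight, blood pressure, pulse, temperature") and adverse events are both reviewed on days 0, 14, 28, 56 and 70: 5 visits, 4 of them dosing visits.
- Adverse events without vitals are reviewed on days 98 and 126: 2 contacts.

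Surveillance on treatment therefore exists and includes weight and temperature. It can pick up TB once signs appear. It cannot do what an entry test does, which is to act before the first dose.

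**The case against.** The strongest reply is that the permissive reading is the less natural one. The PPD is the named test and the film sits in parentheses. The schedule gives everyone a PPD at the same visit as an eligibility assessment, and gives nobody a film. Read together, a positive PPD could simply be a failed screening test and the film a substitute when no PPD is available. For the gap to matter, someone would have to order an unscheduled film after a positive PPD and let it decide. Exclusion 19 can reach such a case, and the protocol's own mention of TB should prompt its use. Patients are also watched: "Patients will be assessed at office visits and by continuous availability by phone for adverse events".

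Much of this stands. The fallback reading is plausible, the backstops are real and surveillance on treatment is not absent. But no condition on the film is written, and both backstops leave the decision to judgement.

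Three stronger inferences are tempting, and the documents do not support them:

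- *That the protocol intends a film to outrank a positive PPD.* The text permits that result but does not state it as the intention.
- *That exclusion 8 contradicts itself, because recent contact or travel excludes whatever the film shows while a positive PPD does not.* The two parts are cumulative and can both be applied. Excluding on history says nothing about how two tests rank.
- *That a particular number of women would be exposed.* The documents give no rate of PPD positivity, and the history part of exclusion 8 already removes some of the women most likely to test positive.

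It is also fair to say that the protocol does not discuss latent infection. It supports only the point that TB is a recognised risk of treatment.

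**Conclusion.** The point holds in a limited form. As worded, exclusion 8 lets a woman with a positive day -7 PPD and a clear film meet the TB criterion, provided the history part does not apply to her. Whether she is then randomised rests on the investigator.

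This is more than a missing detail, because a site that follows the rule exactly can admit her. The number affected cannot be estimated from the documents and may be zero, so no size is attached beyond the structural facts: for any such woman on active drug, 4 scheduled doses and no further TB test until day 126.

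The conclusion rests on the visible text. A figure within the exclusion list and the study flow chart are not shown, and either could add a condition. It should be corrected, with medium confidence.

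**What to change.** Replace the test requirement in exclusion 8 with:

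> *The re-evaluation PPD must be negative. A negative CXR does not override a positive PPD. A negative CXR may substitute only where a PPD cannot be done or read.*

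The history, contact and travel exclusions stay as they are and still apply to women who enter on a film. If a fallback was what the sponsor meant all along, this simply writes it down.

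No new procedure is needed, since the PPD is already scheduled for everyone. The cost is that a few PPD-positive women with clear films, some possibly false positives, become screen failures. One limit remains: for women in whom a PPD cannot be done or read, the film is still the only TB test before dosing.

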### Purpose and Study Background

Interstitial cystitis/ bladder pain syndrome (IC/BPS) is a chronic, debilitating bladder disease characterized by suprapubic pressure or pain accompanied by urinary frequency and urgency, in the absence of an identifiable cause. Population based studies have demonstrated a prevalence rate of 3 to 12 percent among women and 2 to 4 percent for men. The symptoms of IC/BPS result in a poor quality of life with sleep dysfunction, sexual dysfunction, depression, anxiety, and stress.

The pathogenesis of IC/BPS is undefined. Treatments of IC/BPS have been empirical and inadequate. Narcotics are the most commonly prescribed medication. The direct cost of medical care for IC/BPS patients is > \$11,000 per year. There are also the indirect costs to society including work absenteeism and decreased productivity. Investigation of novel therapies is needed.

IC/BPS has been postulated to be one of the autoimmune diseases. Like autoimmune diseases, IC/BPS affects more women than men. Infection and stress worsen both conditions. Pregnancy improves symptoms for both IC/BPS and autoimmune diseases. There is a clinical concordance of IC/BPS with other established autoimmune diseases. IC/BPS as an autoimmune disease is not a new theory. In 1938 Fister recognized the clinical and histopathologic similarities between IC/BPS and lupus erythematosus. In the 1980 review article, Oravisto viewed IC/BPS as an autoimmune disease due to the very chronic course of the disease, the absence of infection, the pathological findings, the common occurrence of antinuclear antibodies, and the response to certain modalities of treatment. In Immunosuppressive drugs including methotrexate, prednisone, and cyclosporine A, routinely used to treat autoimmune diseases, have shown efficacy in selected IC/BPS patients. There are more than 80 different documented autoimmune diseases affecting every organ and tissue in the body. IC/BPS may be the autoimmune disease of the bladder.

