# **Estimated enrollment** 42 patients

After subjective evaluation of efficacy and safety in the initial 30 patients, the total study sample size will be 42 study patients.

Previous IC/BPS studies demonstrated an approximate 20% placebo response rate. Monotherapy response rate of certolizumab pegol in rheumatoid arthritis was 45%. To achieve an 80% power using 2:1 randomization and a 2-sided p = .05 a minimum of 39 subjects was required. The sample size was increased by 3 subjects to account for potential participant withdrawals.

Arms	Assigned Intervention					
Group 1: Experimental	Biological: Certolizumab pegol (Cimzia) 400 mg pre-filled syringe loading dose given subcutaneously at week 0, 2, and 4 followed by a maintenance dose at week 8					
Group 2: Placebo Comparator	Placebo: given subcutaneously at week 0, 2, 4, and week 8					

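### Exclusion 10 bars TNF-alpha inhibitors, cyclosporine and corticosteroids only when taken for interstitial cystitis, so a woman on one for another disease can be randomised, with only a discretionary backstop

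*Protocol*

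**What the plan says.** Item 10 of the protocol's Exclusion criteria covers "Patients taking the following treatments for interstitial cystitis at Screening: Intravesical BCG, corticosteroid therapy, cyclosporine, or TNF-alpha inhibitors". The indication governs all four treatments listed.

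Other text that bears on the point:

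- Protocol, Purpose and Study Background: "There is a clinical concordance of IC/BPS with other established autoimmune diseases". No rate is given. The same section says that methotrexate, prednisone and cyclosporine A are used routinely in autoimmune disease and have helped selected IC/BPS patients.
- Protocol, Exclusion criteria, item 2: "Symptoms are relieved by antimicrobials, antibiotics, or other medications for IC/BPS". This too is tied to drugs given for IC/BPS.
- Protocol, Exclusion criteria, item 19: "Other severe acute or chronic medical or psychiatric condition or laboratory abnormality that may increase the risk associated with study participation". The sentence continues to administration of the investigational product and to interference with interpreting the results, and leaves the decision to the investigator.
- Protocol, Inclusion Criteria, item 12: "Never treated with cyclophosphamide". This drug restriction has no indication attached.
- Protocol, Study Design: "all eligible IC/BPS patients will be randomized in a blinded fashion to receive in a 2:1 ratio".
- Protocol, Trial Schedule: a medication review at screening, re-evaluation, baseline and each clinic visit to week 10, with no rule stating what it should trigger.

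**The concern.** The trial tests whether blocking TNF-alpha relieves IC/BPS. For that question it does not matter why a patient takes a TNF-alpha inhibitor. One prescribed for arthritis acts on the same target as one prescribed for the bladder. A woman already taking one has little room to show an added effect of certolizumab, and if she is allocated placebo she is not a comparator free of the drug class. Urine TNF-alpha, a secondary outcome compared with baseline, would start from a value already under treatment.

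All of this pulls the arms together. The planned placebo arm has 14 women, and the SAP has no adjustment or sensitivity analysis for concomitant immunosuppressants, so the analysis would not reveal or correct the dilution.

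**Working it through.** **Step 1: does any criterion close the gap?**

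| Provision | Applies to these drugs taken for another disease? |
|---|---|
| Exclusion 10 | No; limited to interstitial cystitis as the indication |
| Exclusion 2 | No; limited to relief from IC/BPS medication |
| Named disease exclusions (diabetes, cancer, neurologic disease, specified infections) | No; rheumatoid arthritis or Crohn's disease, for example, is not named |
| Exclusion 19 | Possibly; needs a severe condition or a laboratory abnormality, and the investigator's judgment |
| Medication review (Trial Schedule) | Shows the drug to the investigator, but has no rule attached |

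The documents contain no list of prohibited medication and no washout for these drugs. The cyclophosphamide criterion shows that the protocol can bar a drug whatever the indication.

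**Step 2: the plan's own figure.** Exclusion 10 carries no number. The illustration below uses the planning rates, so the sample-size statement needs checking first. Its inputs are 20% on placebo ("Previous IC/BPS studies demonstrated an approximate 20% placebo response rate"), 45% on active, 2:1 allocation, two-sided 0.05 and 80% power, with a stated minimum of 39.

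- Pooled rate: (0.20 + 2 × 0.45)/3 = 0.3667.
- Placebo n = [1.960 × √(1.5 × 0.3667 × 0.6333) + 0.8416 × √(0.20 × 0.80 + 0.45 × 0.55/2)]² / 0.25²
- = [1.157 + 0.448]² / 0.0625 = 41.2, rounded up to 42. The total is 3 × 42 = 126.

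The stated 39 does not reproduce. That is a separate matter, but it explains why power below starts near 33% and not at 80%.

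**Step 3: size of the dilution.** Assumptions: a share f of entrants is affected, equally in both arms, and affected women gain nothing from study drug, responding at 20% in either arm. Then:

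- placebo rate = 0.20
- active rate = 0.45(1 − f) + 0.20f
- difference = 0.25(1 − f)

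Power is the summed probability of all 28:14 outcomes with two-sided Fisher p ≤ 0.05.

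| f | Affected of 42 | Active rate | Difference (points) | Power |
|---|---|---|---|---|
| 0 | 0 | 45.0% | 25.0 | 33.2% |
| 2.4% | 1 | 44.4% | 24.4 | 31.8% |
| 5% | about 2 | 43.75% | 23.75 | 30.4% |
| 10% | about 4 | 42.5% | 22.5 | 27.6% |
| 20% | about 8 | 40.0% | 20.0 | 22.4% |

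**Step 4: sensitivity to the assumption.** If affected women instead responded at 45% in both arms, the placebo rate would be 0.20 + 0.25f, and power would be 27.0% at f = 10% and 21.6% at f = 20%. The size is much the same. Step 3 is preferred for the reason given in the objection.

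**The case against.** The strongest reply is exclusion 19. Read to its end, it covers both extra risk from the investigational product and interference with interpretation. An autoimmune disease needing a TNF-alpha inhibitor or cyclosporine could well be judged severe, and the investigator sees the medication three times by baseline. This stands in part: entry is permitted, not assured. But the protection depends on case-by-case judgment, is triggered by a condition and not by a drug, and is weaker for a mild condition treated with corticosteroids.

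A reader might also infer more than the documents support:

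- **That such patients are to be expected.** The background section claims concordance with autoimmune disease. It gives no rate for it and none for current use of these drugs. Possible is the right word, and the number may be zero or one.
- **That placebo patients on these drugs would respond at the active rate.** The example wording of the global response assessment asks about change since the trial began. These women must still score at least 18 on the O'Leary-Sant indexes and must not have improved at re-evaluation. Any benefit from an established drug would already be in their baseline. Nothing in the documents gives corticosteroids or cyclosporine the certolizumab response rate either.
- **That the documents show a hazard from two TNF-alpha inhibitors together.** They do not discuss combined use. Serious infection appears among the stopping criteria, but without that link.

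On the remedy, it is fair to object that item 10 gives no route for corticosteroid therapy, so dropping the indication for every listed drug would leave inhaled, topical and short-course use undefined.

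**Conclusion.** The gap is real. As written, exclusion 10 admits women already taking the drug class under test, provided the indication is not interstitial cystitis, and no other criterion bars them outright. Exclusion 19 narrows the gap without closing it.

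The likely effect is dilution. Under the no-added-benefit assumption, exact Fisher power at 28:14 falls by 1.4 points (33.2% to 31.8%) with one affected woman in 42, by 5.6 points at 10% and by 10.8 points at 20%. The share affected is assumed throughout, and the result also rests on the planning rates of 20% and 45% and on an equal share in each arm. The low starting power comes from the sample size, not from this criterion.

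The documents do not support saying that the trial will be materially biased. They support saying that a stated rule permits an avoidable dilution of unknown frequency, and that a small change in wording removes most of it.

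**What to change.** - Remove the indication limit in exclusion 10 at least for TNF-alpha inhibitors, so that current use for any disease excludes. Check it at the medication reviews already scheduled at screening, re-evaluation and baseline, before randomisation.
- For cyclosporine and corticosteroids, the sponsor should state whether the indication limit is intended and which routes of corticosteroid count. This review does not set that rule.
- The sponsor should also state how these drugs are handled if they are started between screening and week 18.

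The cost is a few words in one criterion, no new procedure, and slightly narrower eligibility. How much narrower cannot be calculated, because the documents give no frequency of use.
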